10.5 Pregnancy Reporting

A pregnancy will not be reported as an AE and is not an exclusionary condition for this surveillance study

10.6 Review of Safety Information

10.6.1 Medical Monitor Review

The DAIT/NIAID Medical Monitor will receive monthly reports from the Statistical and Clinical Coordinating Center (SACCC) compiling new and accumulating information on AEs and SAEs recorded by the study site(s) on appropriate eCRFs.

The DAIT/NIAID Medical Monitor will also assess whether a study stopping rule has been met and will recommend either halting of the study for review of the safety information or study termination.

11. Statistical Considerations and Analytical Plan

11.1 Overview

A prospective longitudinal cohort of children and their families will allow us to estimate the incidence of SARS-CoV-2 infection and investigate the association of risks factors for infection while accounting for follow-up and censoring. This study will permit us to gain insights into the complex interaction of SARS-CoV-2 exposure, particularly within families, with participant sex, age, susceptibility, immunological profiles and clinical outcomes.

11.2 Analysis Plan

Population description

Baseline characteristics of 2000 index children and their families that include age, sex, household members, co-morbidities, proportion with evidence of SARS-CoV-2 infection at baseline, and follow-up will be described using standard statistical techniques such as proportions for categorical variables and means and standard deviations (SD), or medians and interquartile ranges as appropriate.

Primary outcome: The cumulative incidence of SARS-CoV-2 RNA detection in nasal samples among index participants and their household contacts over the study period

Time to event analyses will be conducted among participants that are SARS-CoV-2 serologically negative at entry. We will use Kaplan-Meier cumulative morbidity curves for the primary analysis. The primary endpoint will be calculated at the end of follow-up or fate defined as follows. Follow-up time will be the time from entry until the first of the following events:

- Tests positive for SARS-CoV-2 RNA in nasal samples
- Is lost to follow-up or withdraws from the study
- End of study (24 weeks)

Fate at the end of follow-up will be:

- 1 (positive): if the patient tests positive for SARS-CoV-2.
- 0 (censored): if the patient has no evidence of having had disease by the end of follow-up.

Attack rates

SARS-CoV-2 attack rate per person-week will be calculated. Attack rates within families will also be estimated.

Secondary outcome: time to the index participants and their household members with detectable SARS-CoV-2-specific antibodies in serum over the study period.

Cox regression on seroconversion status at 24 weeks: Hazard ratios will be modeled using Cox Regression to compare demographic and clinical factors to the time to detectable SARS-CoV-2-specific antibodies in serum.

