2.2. Secondary Objectives

- a. Determine SARS-CoV-2 antibody development in children and their household members.
- b. Compare SARS-CoV-2 infection status (detection of viral RNA in nasal secretions) and virus-specific antibody development for children with asthma and other atopic conditions (e.g. eczema) versus children without asthma or other atopic conditions.
- c. Determine mucosal immune responses to SARS-CoV-2 infection through gene expression profiling and examine whether these responses are influenced by the presence of asthma or other atopic condition.
- d. Determine whether topical, systemic, or inhaled steroids use, as directed by their care provider, modify the risk of SARS-CoV-2, the severity of infection, or expression of the SARS-CoV-2 receptor.
- e. Determine whether baseline demographic and environmental factors, such as age, sex, race, history of influenza vaccination, rural versus urban living, medications (such as ACE inhibitors), and smoking exposure modify the risk of SARS-CoV-2 infection or the severity of infection.

- f. Assess whether a history of RSV infection or bronchiolitis during infancy modifies severity of SARS-CoV-2 infection.

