3.1. Description of Study Design

This is a prospective surveillance study in which subjects that are currently enrolled in NIH-funded studies (index participant) and their household contacts, including caregiver(s) and possibly a sibling, will be asked to enroll in the SARS-CoV-2 surveillance study. A minimum of 2 family members (index participant and a caregiver) and up to a maximum of 4 total members (additional caregiver and/or sibling) will be enrolled per family. The enrollment goal is approximately 2000 families. The enrollment period will be approximately 8 weeks, and each participant will participate for a minimum of 6 months with possible extension of the observation period. During the study, biological samples will be collected by the family at pre-determined intervals and symptom and exposure surveys will be completed remotely via a smart phone, on-line, or phone communications at the time the biological samples are collected (Figure 3.1 Study Overview). The Schedule of Events (Table A) provides more complete details of the study events and timing of these events. All biological samples (e.g. nasal swabs, peripheral blood, stool) will be collected by the caregiver at home using materials provided to the family. Peripheral blood will only be collected from participants 2 years of age and older. At the end of study, additional samples (e.g. nasal secretion and/or saliva samples) may be collected by the family or study staff at a site visit, if feasible.

If any member of the household develops symptoms compatible with COVID-19, the family will be instructed to complete a symptom survey for the affected household member. If completion of the symptom algorithm meets a study-specified threshold, this will be considered the first illness event for the family/household and an additional nasal swab will be collected from all study participants in the household and an additional stool sample (via swab) will be collected from the affected household member if they are a study participant. Blood will be collected from all study participants that are 2 years of age and older three weeks following this first illness event during the study period. Additional nasal swabs and stool samples will be collected from the index participants with every illness that meets the study-specified symptom threshold. For family members other than the index participant, additional samples associated with illnesses will be collected with the first illness event only.

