3.2. Primary Outcome

The cumulative incidence of SARS-CoV-2 RNA detection in nasal samples among index participants and their household contacts over the study period.

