3.3. Secondary Outcome(s)

- a. The percent of index participants and their household contacts with detectable SARS-CoV-2-specific antibodies in serum over the study period.
- b. The cumulative incidence of SARS-CoV-2 detection in nasal samples among index participants with asthma and other atopic disease over the study period as compared to index participants without any atopic disease.
- c. The percent of index participants with asthma and other atopic disease with detectable SARS-CoV-2-specific antibodies in serum over the study period as compared to index participants without any atopic disease.
- d. Changes in the nasal transcriptome that are associated with detection of SARS-CoV-2 in nasal samples among index participants and their household contacts over the study period.
- e. Changes in the nasal transcriptome that are associated with detection of SARS-CoV-2 in nasal samples among index participants with asthma and other atopic disease over the study period as compared to index participants without any atopic disease.
- f. Symptoms (including upper and lower airway, gastrointestinal, and systemic symptom as assessed via questionnaires) that are associated with detection of SARS-CoV-2 in nasal samples among index participants and their household contacts over the study period.
- g. The cumulative incidence of SARS-CoV-2 detection in nasal samples among index participants using topical, systemic, or inhaled steroids during the study period as compared to index participant that are not using topical, systemic, or inhaled steroids.
- h. The association of baseline demographic and environmental factors or history of bronchiolitis with the cumulative incidence of SARS-CoV-2 detection in nasal samples among index participants and their household contacts over the study period.

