9.2. Participant Stopping Rules and Withdrawal Criteria

Participants may be prematurely terminated from the study for the following reasons:

- The participant elects to withdraw from all future study activities
- The participant is “lost to follow-up” (i.e., no further follow-up is possible because attempts to reestablish contact with the participant have failed)
- The participant dies
- The Investigator no longer believes participation is in the best interest of the participant
- If the index participant’s enrollment is terminated, the caregivers’ and siblings’ participation will be terminated; however, termination of enrollment of the caregiver or sibling will not result in termination of the index participant

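### Section 11.2 names no variance that allows for within-household correlation, so ordinary 95% limits for the pooled incidence would be too narrow

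*Combined protocol and SAP*

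**What the plan says.** Section 3.2 defines the primary outcome as "The cumulative incidence of SARS-CoV-2 RNA detection in nasal samples among index participants and their household contacts over the study period". Section 3.1 sets the household size: "A minimum of 2 family members (index participant and a caregiver) and up to a maximum of 4 total members".

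For the primary analysis, Section 11.2 states: "We will use Kaplan-Meier cumulative morbidity curves for the primary analysis". Under attack rates it says that the "attack rate per person-week will be calculated. Attack rates within families will also be estimated". For time to detectable antibodies in index participants and household members together, it says: "Hazard ratios will be modeled using Cox Regression to compare demographic and clinical factors".

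No section names an interval method for the Kaplan-Meier estimate, and none names a clustered variance, frailty term, household bootstrap or GEE. Section 11.1 undertakes to account for follow-up and censoring but does not mention household correlation. The within-family attack rate is a separate estimate and supplies no variance for the pooled ones.

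**The concern.** Members of one family are not independent observations here, and the protocol says why. Section 2.3 (objective a) sets out to study transmission between household members, so infections are expected to cluster. Section 6.3.1 has every study participant in the household swabbed when one member's first illness meets the symptom threshold, so detection is linked as well as infection.

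Greenwood, Poisson and default Cox standard errors all treat people as independent. If they are used, the limits for the pooled incidence and the person-week rate claim more precision than the data hold. Section 5.2 gives the purpose of the study as incidence data to inform control of spread, so the overstatement would fall on its main result.

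For Cox regression the direction depends on the factor. A factor that all members share gets limits that are too narrow. A factor that varies independently between members is about right. A factor balanced within households, such as child versus caregiver role, gets limits that are too wide, because the comparison within a family cancels the shared risk and the ordinary standard error does not credit this.

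**Working it through.** **1. The plan's own figures.** Section 11.3 gives Wilson 95% intervals for 2000 family units. The formula is [p + z²/2n ± z√(p(1−p)/n + z²/4n²)] / (1 + z²/n), with n = 2000 and z = 1.96. It gives 2.34–3.84% at 3%, 4.13–6.04% at 5%, 8.76–11.39% at 10% and 18.31–21.81% at 20%. These match the stated limits to rounding, except that the lower limit at 10% is printed as 8.7. They describe one unit per family, not the pooled endpoint.

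**2. Inputs for the pooled endpoint.** From the documents: 2000 families, 2 to 4 members, 95% limits, and 10% incidence as one of the Section 11.3 cases. Assumed: within-household transmission s of 10%, 30% or 50%, and either 2 members in every household or equal shares of 2, 3 and 4.

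**3. Model.** Each member is infected from the community with probability c. Each infected member then infects each susceptible member with probability s, with onward spread. The value of c is solved so that person-level incidence p is 10%.

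**4. Two members, by hand.** p = c + c(1−c)s; P(both) = c² + 2c(1−c)s; ICC = [P(both) − p²] / [p(1−p)]; design effect DE = 1 + ICC.

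- s = 10%: c = 0.0917; P(both) = 0.0084 + 0.0167 = 0.0251; ICC = 0.0151/0.09 = 0.167; DE = 1.167.
- s = 50%: c = 0.0682; P(both) = 0.0047 + 0.0635 = 0.0682; ICC = 0.0582/0.09 = 0.647; DE = 1.647.

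**5. Mixed sizes.** DE = E[(k − mp)²] / [E(m) p(1−p)], where m is household size, k the number infected in the household (exact enumeration) and E(m) = 3.

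**6. Coverage and limits.** Coverage of a nominal 95% interval is 2Φ(1.96/√DE) − 1. Adjusted limits are Wilson limits with n divided by DE.

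| Household size | s | DE | Coverage | Unadjusted limits | Adjusted limits |
|---|---|---|---|---|---|
| 2 (4000 people) | 10% | 1.167 | 93.0% | 9.11–10.97% | 9.04–11.05% |
| | 30% | 1.438 | 89.8% | same | 8.94–11.17% |
| | 50% | 1.647 | 87.3% | same | 8.87–11.26% |
| 2, 3, 4 equally (6000 people) | 10% | 1.445 | 89.7% | 9.27–10.78% | 9.12–10.95% |
| | 30% | 2.351 | 79.9% | same | 8.90–11.22% |
| | 50% | 2.969 | 74.5% | same | 8.77–11.38% |

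The mixed-size design effect is 1.47 to 3.00 at 5% incidence and 1.40 to 2.90 at 20%, so the incidence matters little.

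**7. Check by simulation.** With 2000 mixed-size households and twelve 2-week intervals, Greenwood coverage was 90.2%, 81.7% and 75.5% at 10%, 30% and 50% transmission, against 95.5%, 95.4% and 95.4% with household-clustered variance. For the person-week rate, Poisson coverage was 90.2%, 82.1% and 76.2%, against 94.8%, 95.4% and 95.2%. The mean Kaplan-Meier estimate was 9.94%, 10.02% and 9.96%, so there was no bias. Index-only Kaplan-Meier coverage was 94.2%, 95.4% and 94.8%.

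**8. Cox, no true effect.** Simulation with 1000 families, 20% incidence, ICC roughly 0.3 to 0.4 and only 150 replicates. The ratio is the empirical SD over the mean default standard error.

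| Factor | Ratio, 2 members | Ratio, 4 members | Coverage, 2 and 4 members |
|---|---|---|---|
| Shared by the household | 1.15 | 1.43 | 92.7%, 81.3% |
| Independent between members | 1.02 | 1.02 | 94%, 94% |
| Balanced within the household | 0.83 | 0.67 | 98.7%, 99.3% |

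**The case against.** **No wrong method is prescribed.** Section 11.2 names no interval method at all, and it does not say whether index participants and contacts share one curve. This stands, and it makes the point conditional on ordinary standard errors. But the endpoint is defined over both groups, and even a contacts-only curve can hold up to three people from one family.

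**The planned precision may survive.** With 2000 families analysed, the widest interval above (8.77–11.38%) is no wider than the 8.76–11.39% computed for 2000 units. This also stands. The harm is in reporting tighter limits than the data support, not in an undersized study. A reader might infer that the Section 11.3 intervals are wrong. They are not, since they are stated for family units.

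**The size is assumed.** Many households may enrol only two members. Fewer may be analysed, because the primary analysis is restricted to people seronegative at entry and no blood is taken under age 2. Both would reduce the effect.

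**The Cox example is not spelled out.** The Cox sentence speaks of demographic and clinical factors. The household-shared candidates appear in the Section 2.2 list, "history of influenza vaccination, rural versus urban living, medications (such as ACE inhibitors), and smoking exposure", and Section 3.3 (item h) concerns "The association of baseline demographic and environmental factors or history of bronchiolitis with the cumulative incidence", for which Section 11.2 gives no regression. So Section 11.2 does not expressly put rural versus urban living into the antibody model. The statement about shared factors holds for whichever of them are entered.

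**Linked withdrawal.** Section 9.2 ends the contacts' enrollment with the index participant's: "participation will be terminated; however, termination of enrollment of the caregiver or sibling will not result in termination of the index participant". A reader might infer that this also narrows the limits. It links censoring, not infection. With independent infections and 40% of households withdrawing together at random, two simulation runs gave Greenwood coverage of 94.8% and 94.4%, with SD/SE of 1.01 and 1.02. Withdrawal unrelated to infection is therefore no part of this concern.

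**Conclusion.** The concern holds in a limited form. Section 11.2 leaves the variance open for estimates that combine members of the same household. With ordinary standard errors, nominal 95% limits for the pooled incidence would cover about 93.0% to 87.3% of the time with two members per household, and 89.7% to 74.5% with the mixed sizes. The person-week rate behaves in nearly the same way.

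These figures rest on 10% incidence, assumed transmission of 10% to 50% and assumed household sizes. The direction needs only positive within-household correlation, which the protocol itself anticipates.

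Two stronger readings are not supported. A reader might infer that every Cox interval would be too narrow, but that applies only to factors shared by a household. A reader might also infer that the incidence estimate is biased, but clustering alone does not bias it. The comparisons among index participants in Section 3.3 (items b, c, e and g) have one person per family and need no change. This is worth fixing before analysis but does not threaten the design.

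**What to change.** In Section 11.2, specify:

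- for the pooled Kaplan-Meier limits and the person-week attack rate, a bootstrap that resamples whole households, or a robust variance clustered on household;
- for every Cox model that pools household members, a sandwich variance clustered on household. This corrects the limits in both directions.

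The cost is a few sentences and a standard software option, with no new data. Reported intervals for the pooled incidence become wider. At 10% incidence with the mixed sizes, each limit moves by about 0.15 percentage points (9.27 − 9.12) to 0.60 (11.38 − 10.78). Settling this in advance also removes a choice between narrower and wider intervals after the results are known.

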6.1. Enrollment and Training

Potential study participants (usually the primary care provider for minor children) will be contacted by a member of the clinical research site staff via text, email, or phone call who will direct them to the link to the study HEROS home web page. If interested in participating in the study, the participant/caregiver will be given instructions to view the study web portal. The potential participant will read an information sheet that includes details about the study, study requirements, and study risks, and will provide assurance that each participating family member has read the information sheet and agrees to participate for themselves, index participants, and other family members. The participant will then be directed to complete an electronic registration form and to complete a baseline questionnaire. Once this process is completed, the participant is considered enrolled in the study and will be assigned a unique participant number. All participating family members will be assigned unique participant numbers. Upon completion of these tasks, the sample kit distribution center will mail each household a set of sample collection kits for initiation of bio-sampling.

Once enrolled, the primary contact/caregiver and each participant will be requested to undergo a web-based training that will describe in detail the processes of sample collection and handling. Study staff will be available by phone, Skype, text, or video conferencing for further instructions and clarifications on sample collection procedures.

At Week 18, the primary contact/caregiver will be electronically sent an information sheet that includes details about a study extension that will include collecting 4 additional nasal swabs for a total of 14 nasal swabs over 28 weeks. The information sheet will require that each participating family member attest that they have read the information sheet. The household will have the option to continue with the original visit and sample collection schedule (10 nasal swab collections over 24 weeks), to participate in the study extension with 4 additional nasal swab collections, or to request further information via contact with their local study site.

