6.2. Index participants and Household Contacts Study Assessments

6.2.1 Caregiver-Collected Samples

At the times shown in the Schedule of Events (Table A), the primary contact/caregiver will collect nasal swabs from the index participants and all family members that are enrolled in the study at the beginning of the study (Week 2) and every 2 weeks thereafter for 9 collections, then a final 10th nasal swab collected at the end of the study (total 10 nasal swabs collected over 24 weeks). If the household agrees to participate in the study extension, 4 additional nasal swabs will be collected between Week 18 and Week 28 (Table A). Stool samples via swabs will be collected from the index participants and all family members that are enrolled (starting at Week 2) into the study (Table A). Blood samples will be collected via the OnDemand device from the index participants and all family members that are enrolled in the study and 2 years of age and older (Table A). Nasal secretion and/or saliva samples may also be collected from the index participants and all enrolled family members at Week 24. Samples will be shipped as instructed in the sample kit package. Details of the nasal swab, stool collection, blood collection, nasal secretion, and saliva procedures will be provided in the sample kit package.

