6.4. Sample Collection/Questionnaire Completion Windows

Sample collection and completion of the study questionnaires should take place within the time limits specified in the Schedule of Events (Table A).

Table A. Schedule of Events for All Participants

*The window for sample collection and completion of Symptom and Exposure surveys is (+/-) 4 business days

¹There is no window for the baseline (Week 2) blood collection.

²Additional nasal swab and a stool samples will be collected when a household member shows signs of a viral illness and a study-specified threshold for symptom algorithm has been met. For the first illness, the nasal swab sample will be collected within 24 hours from all study participants, including the affected household member, and a stool sample from just the affected household member. Subsequent illnesses will be assessed only if the index participant is affected; in this case a swab and a stool sample will be obtained within 24 hours only from the index participant.

³A nasal secretion and/or saliva sample may be collected at End of Study.

⁴Nasal swabs will be collected at Week 20, 22, 26 and 28 and Health Check Surveys at Week 19, 21, 23, 25, and 27 from participants that agree to participate in the study extension.

⁵An end of study blood sample will be collected from all study participants that are at least 2 years old at Week 24 or at Week 28, if the participant decided to continue in the study with the original visit plan or agreed to participate in the extension, respectively.

⁶An additional blood sample will be collected from all study participants that are at least 2 years old three weeks after a first illness in the household and a study-specified threshold for the symptom algorithm has been met.

7. Laboratory Assays

- SARS-CoV-2 detection and nasal transcriptomics. RNA extracted from all swabs will be used to perform RT-qPCR for SARS-CoV-2. The remaining RNA and DNA will be stored for possible detection (and quantification) of other respiratory viruses, for generating the host transcriptome response to infection (from airway epithelial and any immune cells that were present on the nasal swab), and for delineating the nasal microbiome at the time the swab was collected.

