12.3 Genomic Data Sharing Policy

DNA from participants in the HEROS study will be stored for analysis that will be limited to studies of SARS-CoV-2 infection. The NIH Genomic Data Sharing (GDS) policy requires deidentified genomic data from a NIH-funded study to be shared via dbGaP. However, GDS provides an exception to allow for controlled access to the data. The protocol chair for HEROS will submit a request for this exception which allows for deposition of summary (high level general) data with a 'controlled access guard' so that a future investigator would need to ask NIAID for permission to access the COVID-19 collected summary data and will be required to indicate that data analysis will be restricted to COVID-19 research.

13. Quality Assurance and Quality Control

The site principal investigator is required to keep accurate records to ensure that the conduct of the study is fully documented. The NIAID Division of Allergy, Immunology, and Transplantation (DAIT) is responsible for regular inspection of the conduct of the trial, for verifying adherence to the protocol, and for confirming the completeness, consistency,

and accuracy of all documented data. On a frequency determined by DAIT/NIAID, a clinical monitor from the SACCC will conduct a review of the conduct of the study by remote data review. Site study staff and participants will complete electronic case report forms and questionnaires online via a web-based electronic data capture system and data will be stored remotely at a central database. Data quality will be ensured through the electronic data capture system's continuous monitoring of data and real-time detection and correction of errors. All elements of data entry (e.g., time, date, verbatim text, and the name of the person performing the data entry) will be recorded in an electronic audit trail to allow all changes in the database to be monitored and maintained. In addition, SACCC data managers and statisticians will monitor data completeness and other elements of data quality throughout the trial and provide periodic reports on data quality.

14. Protocol Deviations

Since this is a Public Healthy Surveillance study and not human subject research, we will not be collecting protocol deviations. Missed samples and incomplete questionnaires are considered missing data.

15. Ethical Considerations

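### The primary Kaplan-Meier risk time is not tied to swabbing, so participants who stay in contact but stop swabbing count as at risk and event-free to Week 24

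*Combined protocol and SAP*

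**What the plan says.** **Risk time.** Section 11.2 sets follow-up as "Follow-up time will be the time from entry until the first of the following events". Three events are listed: a positive nasal RNA test, loss or withdrawal, and "End of study (24 weeks"). Anyone without evidence of disease by then is coded as censored; no negative swab is required.

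**Loss and missed swabs.** Section 9.2 explains loss to follow-up as the case where "no further follow-up is possible because attempts to reestablish contact with the participant have failed". Section 14 says: "Missed samples and incomplete questionnaires are considered missing data". Neither says what a missed swab does to the risk set. Section 11.1 promises to account for follow-up and censoring but gives no rule.

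**Schedules.** Under Section 6.2.1, swabs start at Week 2 and continue "every 2 weeks thereafter for 9 collections, then a final 10th nasal swab collected at the end of the study", that is Weeks 2, 4, ..., 18 and then 24. Under Section 6.1, an extension is offered at Week 18: "The household will have the option to continue with the original visit and sample collection schedule (10 nasal swab collections over 24 weeks") or to add four swabs. Table A, footnote 4 (Section 6.4) places these at Weeks 20, 22, 26 and 28. Section 11.2 does not mention the extension.

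**Entry.** Section 6.1 says, of registration and the baseline questionnaire, "Once this process is completed, the participant is considered enrolled in the study". The first swab and baseline blood come at Week 2. Section 11.2 does not say which date is entry.

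**The concern.** The primary outcome can occur only in a swab. Time without swabs is time in which the event cannot be seen, yet the written rule counts it as observed, event-free time for anyone still in contact. All sampling is done at home by caregivers over 24 weeks, so answering surveys while no longer swabbing is a plausible pattern. The plan's headline incidence and its attack rate per person-week would then fall with the share who stop, and a larger sample would not reduce that error.

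The second strand is smaller. Between Weeks 18 and 24, detection depends partly on the schedule a household chooses. Illness-triggered swabs fill the gap only in part: they need symptoms above a threshold, and household contacts get them at the first household illness event only (Sections 3.1 and 6.3).

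**Working it through.** **The plan's own precision figure.** Section 11.3 gives 8.7-11.4% at 10% with n = 2000. The Wilson interval recomputes to 8.76-11.39%, so the figure reproduces to within 0.1 point. The printed limits give a half-width of (11.4 − 8.7)/2 = 1.35 points, used here as the yardstick.

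**Assumptions, none from the documents except the 10% scenario.** True 24-week incidence 10%, constant hazard, entry at Week 0, swabs that detect every infection while RNA is present, scheduled swabs only, no loss or withdrawal. Hazard = −ln(0.9)/24 = 0.00439 per week.

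**Stopping, closed form.** Let a share f stop after a last swab at week s. Under the written rule nobody leaves the risk set before Week 24 except by an event, so the Kaplan-Meier estimate is the share with a detected event:

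(1 − f) × 0.10 + f × (1 − 0.9^(s/24))

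- f = 20%, s = 8: 0.080 + 0.20 × 0.0345 = 8.7%.
- f = 20%, s = 12: 0.080 + 0.20 × 0.0513 = 9.0%.
- Uniform stopping time, all households on 2-weekly swabs: the last swab is equally likely at 0, 2, ..., 22 weeks, and the mean of 1 − 0.9^(s/24) is 0.0467.
  - f = 10%: 0.090 + 0.0047 = 9.5%
  - f = 20%: 0.080 + 0.0093 = 8.9%
  - f = 30%: 0.070 + 0.0140 = 8.4%

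With censoring at the last swab, and stopping unrelated to risk, the expected estimate is 10.0% in each case.

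**Stopping, simulation.** Swab times vary uniformly within ±5.6 calendar days, standing for the 4-business-day window in Table A. Each swab counts at its nominal week.

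| Share stopping | Written rule, 21- to 28-day RNA | Censored at last swab | Shortfall |
|---|---|---|---|
| 10% | 9.4-9.5% | 9.9-10.0% | about 0.5 |
| 20% | 8.8-8.9% | 9.9-10.0% | about 1.1 |
| 30% | 8.3-8.4% | 9.9-10.0% | about 1.6 |

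Against 1.35 points, only the last row is larger. The attack rate at 20% stopping is 3.9 per 1000 person-weeks under the written rule and 4.3-4.4 with last-swab censoring.

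**Schedule choice, no stopping.** Infections starting in Weeks 18-24 amount to 0.9^(18/24) − 0.9 = 0.924 − 0.900 = 2.4 points. A single swab at Week 24 catches those that began within the RNA-positive period before it: 3/6 = 50% at 21 days, 4/6 = 67% at 28 days, all at 42 days. Swabs at Weeks 20, 22 and 24 catch all of them at these durations. If 50% of households decline the extension:

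- 21 days: 2.4 × 0.50 × 0.50 = 0.6 points lost
- 28 days: 2.4 × 0.33 × 0.50 = 0.4 points lost
- 42 days: none

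Simulations with the collection window give 9.3%, 9.6% and 9.9%. The loss is about 0.3-0.7 points at 21-28 days and little at 42 days, inside the planned half-width. If illness swabs caught 40% of infections, it would be 0.4 (21-day) or 0.2 (28-day).

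**The case against.** **The stopping rate is undocumented.** Lost and withdrawn participants are already censored, so the 10-30% must be people who stop swabbing while still in contact, and the documents give no rate for them. This stands. It limits the size, not the textual gap.

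**The outcome is detection, not infection.** The shortfalls are measured against infection incidence, whereas Section 3.2 defines RNA detection. That weakens the schedule strand. It does not rescue the stopping strand, because unswabbed time is not observed for detection either.

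**A late Week 24 swab.** A reader might infer that a 24-week cut discards Week 24 swabs taken late but in window. The documents do not support this. Section 6.2.1 places the tenth swab at study end, and Section 6.4 says "The window for sample collection and completion of Symptom and Exposure surveys is (+/-) 4 business days". The natural reading includes that swab; explicit wording is only tidier.

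**Group comparisons.** A reader might also infer that the atopy comparison is biased and should move to Week 18. That would need opt-in to differ by atopy, which the documents do not say. Even an illustrative 30% against 70% declining gives a ratio of only 0.96-0.97. With an assumed 1000 children per group, the full-data log ratio has standard error 0.140 and bias 0.041, so root mean square error √(0.140² + 0.041²) = 0.146. A Week 18 comparison has standard error 0.156, and one without the Week 20 and 22 swabs 0.144. Neither is a clear gain, so these belong in sensitivity analyses.

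**Swab-based censoring drops some real events.** Section 11.2 counts any positive, and an illness swab can be positive after scheduled swabbing has stopped. With 20% stopping, 50% declining and 40% illness capture, about 4% of observed positives would be set aside. The estimate stays at 9.6-9.8%, but the exclusion must be declared.

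**Conclusion.** The concern holds as a defect in the written censoring rule. Followed literally, Section 11.2 counts unswabbed time as event-free risk time, and nothing in Section 9.2, 11.1 or 14 corrects this. It pulls both the cumulative incidence and the attack rate downward. At a true 10%, the shortfall is about 0.5, 1.1 or 1.6 points for 10, 20 or 30% stopping, under the assumptions listed above. The schedule choice is secondary.

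A reader might conclude that the reported incidence will be materially too low. The documents do not support that: they give no stopping share, opt-in share or RNA duration, and the 10% and 20% cases lie inside the planned precision. Infections already present at entry in seronegative participants would also push the estimate up, by about 0.4 points (21-day RNA) or 0.8 (28-day), so the net direction is conditional. Confidence is high in the gap and conditional in its size. It should be fixed before analysis.

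**What to change.** Amend Section 11.2 as follows.

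1. **Censoring.** *Event-free participants are censored at their last resulted negative scheduled swab. A scheduled swab taken in its window counts at its nominal week, including Week 24. Participants with no resulted swab contribute no risk time.* Compute attack-rate person-weeks by the same rule.
2. **Illness-triggered positives.** State that those arising after scheduled swabbing has stopped are excluded from the main estimate. Add a sensitivity analysis that counts them, as Section 11.2 now does.
3. **Schedules.** Keep the Week 24 estimate, and the group comparisons over the study period, as the main analyses. Add as sensitivity analyses the cumulative incidence to Week 18, where all households share one schedule, and a Week 24 estimate without the Week 20 and 22 swabs.
4. **Dates.** Name the entry date.

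**Cost.** Plan wording and a little more analysis; no new samples. With 2000 index children at 10%, the half-width goes from 1.31 points without stopping to about 1.4 at 20% stopping. The written rule's 1.25 at 20% stopping is narrower only because unobserved time is counted.

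**Limits.** The rule assumes stopping is unrelated to infection risk. If stoppers had 0.67 or 1.5 times the hazard of others (20% stopping, 50% declining, 21-day RNA), it would give 9.7% or 9.0% against 9.3% without stopping; the written rule would give 8.7% or 8.1%. It hardly repairs scattered missed swabs: with 20% missed at random, the estimate moves only from 8.7% to 8.9%.
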